5.1.3.1 Part 1, M8891 Single Agent, Solid Tumors

The treatment period will begin at the first dose of M8891 in Cycle 1 Day 1 and consist of consecutive 21-day cycles of continuous once daily M8891 monotherapy under fasting conditions.

Subjects will receive M8891 at the pre-specified dose level until disease progression, unacceptable toxicity, withdrawal of consent, or any criterion for withdrawal from the study (Section 5.5.2).

If the subject tumor evaluation indicates that the disease is slowly progressing according to the CT scan as per Response Evaluation Criteria in Solid Tumors (RECIST) v1.1 criteria (a growth of the target lesions of less than 35% from baseline and no new lesions, or new lesion(s) smaller than 1 cm; bone metastatic lesions or lesions treatable with local radiotherapy would also fall in the same category), but the subject performance status is the same as baseline and there are no safety concerns, i.e. no ongoing symptomatic events Grade 2 or higher in severity, treatment may be continued for another 2 cycles to the next tumor evaluation, upon evaluation by the treating physician and after the continuation of therapy has been discussed with the Sponsor.

CCI

In principle, dose escalation of M8891 will proceed according to the decision of the SMC to the MTD, or the SMC may decide ceasing further dose escalation following review of safety, tolerability, PK and CC results.

The selection of the recommended dose for the expansion cohort of M8891 is based on the following criteria derived from the PK/C_{max} model:

CCI

The MS100015-0019 trial employs a Bayesian two-parameter logistic regression model with overdose control to assist the SMC with dose selection (Babb 1998; Neuenschwander 2008). The model incorporates nonclinical toxicity and observed DLT information from all previously completed dose escalation cohorts to provide a dose recommendation for the next dose cohort. The SMC will decide on the next dose level based on the Bayesian model, safety, PK analyses CCI [REDACTED] Dose escalation will start at 7 mg administered once daily.

A preselected set of doses (8 projected escalation steps with doses of 7, 12, 20, 35, 60, 100, 150 and 210 mg QD) are considered by the model, although doses may be skipped and/or others that are not part of the pre-specified set may be chosen as well. Sequential cohorts of 3 subjects at the same dose level will be used.

At each dose level, and following initiation of dosing, the first subject in each cohort will be observed for DLTs for at least 7 days before commencing dosing of 2 subsequent subjects. The SMC may choose to reduce or extend 7-day intra-patient observation interval up to \pm 7 days based upon safety observations. The DLT assessment period is Cycle 1 (= 21 days). Subjects who missed more than 4 cumulative days of treatment in the first cycle for any reason other than a DLT will not be considered in the Bayesian model. An SMC meeting with selection of dose for next cohort will also be held if only data from 2 subjects of a 3 subject cohort are available (e.g. if a subject missed more than 4 cumulative days of treatment in the first cycle for any reason other than a DLT). Subject replacement will be considered based on reason for withdrawal and safety evaluation of cumulative data i.e. current and previous cohort data if applicable.

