Subjects will receive M8891 at the assigned dose level and cabozantinib at 60 mg QD until disease progression, unacceptable toxicity, withdrawal of consent, or any criterion for withdrawal from the study (Section 5.5). Unacceptable toxicity in Part 2A is defined as AEs that meet the DLT criteria (Section 5.1.3.3) regardless of when they occur during treatment. An SMC meeting will be held after every cohort to evaluate the safety and tolerability of the combination and to decide on the dose of M8891 for the next cohort.

During Part 2A the selection of the dose will only influence the dose of M8891. Cabozantinib will be given at the approved dose of 60 mg QD. Subjects who develop a DLT during the DLT period, will discontinue treatment with M8891 and will be withdrawn from the study. It will at the Investigator's discretion to continue treatment with cabozantinib or not. The SMC will meet after the completion of each cohort, evaluate the safety of M8891 (combined with cabozantinib), and decide on the recommended dose of M8891. During the treatment phase of the study, guidance for M8891 dose reduction for safety and tolerability is provided in Section 5.1.3.5. Reduction of cabozantinib dose in accordance with the USPI (Refer also to Section 5.1.3.5) will be at the Investigator's discretion based on clinical judgement for safety and tolerability.

At each dose level, the first subject will be observed for DLTs for at least 48 h before commencing dosing of 2 subsequent subjects. The DLT assessment period for Part 2A is the first Cycle (= 22 days, 21 days of M8891 combined with cabozantinib, preceded by 1 day of M8891 alone) of study treatment. Subjects who do not receive at least 80% of the planned cumulative dose of both treatments in Cycle 1 for any reason other than a DLT will not be considered in the DLT evaluation per Bayesian model. Subjects will be replaced to reach a minimum of 2 evaluable subjects per cohort.

In cases where enrollment of the last subject in a dosing cohort is delayed, the SMC may decide (based on available data) upon enrollment and dose for the next dosing cohort before all subjects in a cohort have completed the DLT period. For this subject, the SMC will consider all available data (and any subsequent emerging data) at a subsequent meeting. An ad-hoc meeting will be convened if this subject experiences a DLT.

CCI

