5.1.3.3 Dose-Limiting Toxicities

DLTs will be used to determine dose escalation and de-escalation as well as determination of MTD. A DLT is any Grade ≥ 3 non-hematologic AE or any Grade ≥ 4 hematologic AE according to the National Cancer Institute – Common Terminology Criteria for AEs (NCI-CTCAE) version 4.03, occurring during the DLT observation period (Cycle 1) that is judged not to be related to the underlying disease or any previous or concomitant medication. DLTs, along with other safety information (including AEs assessed as not related to the underlying disease or other concomitant medications), will also be used to determine RP2D for M8891 as single agent (Part 1) and the RDE/MTD for M8891 combined with 60 mg of cabozantinib QD (Part 2A).

- DLTs are defined as any of the following pre-defined set of AEs observed in the first treatment cycle for Part 1 (21 days) and Part 2A (22 days; 21 days of M8891 combined with cabozantinib, preceded by 1 day of M8891 single agent) based on predefined set of AEs and judged to be M8891 (or M8891 combined with cabozantinib) related or clinically relevant, (excluding events to be related to underlying disease, medical history or concomitant medications/ procedures in the opinion of the SMC).
- Any death not clearly due to the underlying disease or extraneous causes
- A treatment-emergent AE (TEAE) attributable to study drug that in the opinion of the SMC is of potential clinical significance such that further dose escalation would expose subjects to unacceptable risk
- Evidence of treatment related hepatocellular injury, e.g. alanine aminotransferase or aspartate aminotransferase (ALT/AST) $> 3 \times$ upper limit of normal (ULN) with elevation of serum total bilirubin to $> 2 \times$ ULN, without initial findings of cholestasis (elevated serum alkaline phosphatase) or other apparent clinical causality, including liver metastasis
- Any Grade 4 liver enzyme elevation that is possibly drug related should be considered a DLT. In case of Grade 3 or 4 values, the subject must be monitored until recovery to \leq Grade 2
- Grade 4 neutropenia lasting > 5 days or Grade ≥ 3 neutropenia with fever (temperature of $> 38.3^{\circ}\text{C}$)
- Grade 4 thrombocytopenia lasting > 5 days or Grade ≥ 3 thrombocytopenia with clinically significant bleeding
- Any treatment interruption > 7 days or $> 30\%$ of total dose in Cycle 1 due to AEs not related to the underlying disease or concomitant medication

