5.1.3.5.2 Cabozantinib

The approved dosage of cabozantinib in mRCC is 60 mg once daily without food until the subject no longer experiences clinical benefit or experiences unacceptable toxicity. In Part 2A, cabozantinib will be used at the approved 60 mg free-base equivalent (FBE) daily dosage. After completion of the DLT period in Part 2A and in all cycles of Part 2B, the dose of cabozantinib can be adjusted to 40 mg and then 20 mg to manage AEs (Section 6.5.5). Subjects unable to tolerate a daily dose of 20 mg should discontinue study treatment.

The following should be taken into consideration in decisions regarding cabozantinib dose modifications (reductions or interruption):

- As a general approach all AEs should be managed with supportive care at the earliest signs of toxicity (Table 9 and Table 10). Should this be ineffective, dose reductions or interruptions should be considered to prevent worsening of toxicity.
- The assigned dose for cabozantinib is 60 mg QD. Two dose reduction levels of cabozantinib are permitted (Table 9) if appropriate.
- Dose modification criteria for cabozantinib are shown in Table 10. Dose reductions and/or interruptions should be implemented for unacceptable toxicity. Doses may be modified at any time while on study.

- Dose modifications or interruptions may also occur in the setting of lower grade toxicity than defined in Table 10, if the Investigator feels it is in the interest of a subject's safety and will optimize drug tolerability.
- Interruption of cabozantinib treatment for AEs may occur at any time (except from Cycle 1 in Part 2A) per Investigator discretion. If treatment is interrupted due to AEs for more than 6 weeks, cabozantinib should be discontinued.
- Dose interruptions for reason(s) other than AEs (e.g. surgical procedures) can be longer than 6 weeks but require Sponsor approval. The acceptable length of interruption will depend on agreement between Investigator and the Sponsor.

Table 9 Dose Reductions of Cabozantinib

Assigned dose	First Dose Level Reduction	Second Dose Level Reduction
60 mg cabozantinib oral QD	40 mg cabozantinib oral QD	20 mg cabozantinib oral QD

QD: Once daily.

Cabozantinib should be discontinued if a QD dose of 20-mg cabozantinib (minimum dose) is not tolerated.

Table 10 Dose Modifications of Cabozantinib for Treatment Related AEs

CTCAE v. 4.03 Grade	Recommended Guidelines for Management ^a

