8.4 Analysis Sets

For purposes of analysis, the following populations are defined in Table 13.

Table 13 **Analysis Sets**

Population	Description
Screening	All subjects who sign informed consent
Dose Escalation	All subjects treated in dose escalation cohorts who either Part 1: 
• did not miss > 4 cumulative days of planned doses of M8891 in the first cycle of the dose escalation part or• who experienced a DLT Part 2A and 2B: 
• Received at least 80% of the planned cumulative dose of each treatment in the first cycle of the dose escalation part or• who experienced a DLT
Safety	The Safety Analysis Set will include all subjects who receive at least one dose of trial treatment.
Pharmacokinetic	All subjects from the safety analysis set without major protocol deviations/violations or events that would affect PK. Subjects in the PK analysis set must have received at least 1 dose of M8891, and M8891 combined with cabozantinib and have sufficient M8891/cabozantinib plasma concentration data to enable the calculation of at least one PK parameter. Sufficient concentration data is defined as at least 3 valid, post-dose concentration points in the PK profile to obtain any PK parameter.
Pharmacodynamics in WBCs	All subjects who received at least one dose of M8891 and provide the pre-dose and at least one post-dose WBC assessment. (Only for Part 1 of the study.)
CC1	

PK: Pharmacokinetic; WBC: White blood cell.

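### A subject who misses 5 or 6 Cycle 1 doses because of an adverse event can be neither a DLT nor DLT-evaluable, and leaves the Bayesian model by default without any required SMC classification

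*Protocol*

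**What the plan says.** **When lost dosing is a DLT.** Protocol Section 5.1.3.3 counts an interruption of more than 7 days, or of more than 30% "of total dose in Cycle 1 due to AEs not related to the underlying disease or concomitant medication".

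**When lost dosing removes a subject.**
- Part 1 (Section 5.1.3.1, repeated in 8.5.3.1 and Table 13): for the model, a subject having "missed more than 4 cumulative days of treatment in the first cycle for any reason other than a DLT will not be considered". The window is stated as "The DLT assessment period is Cycle 1 (= 21 days").
- Part 2A (Section 5.1.3.2.1): subjects that "do not receive at least 80% of the planned cumulative dose of both treatments in Cycle 1 for any reason other than a DLT" are left out. The window is 22 days of M8891, of which 21 are with cabozantinib.
- Table 13 in Section 8.4, under a label naming Parts 2A and 2B, sets the condition "Received at least 80% of the planned cumulative dose of each treatment in the first cycle", or a DLT.

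**Replacement.** Part 2A replaces subjects only up to two evaluable per cohort. Section 5.1.3.4 asks for three subjects treated, not evaluable, at the MTD/RDE.

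**Part 2B.** Section 5.1.3.5.2 states that "in all cycles of Part 2B, the dose of cabozantinib can be adjusted to 40 mg and then 20 mg to manage AEs".

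**SAP, Part 1.** Table 1 in SAP Section 8.2 excludes subjects with more than 4 missed days only if the reason was not safety. Item 604 in SAP Appendix 18.1 instead flags, as a clinically important deviation, more than 4 missed administrations without a DLT.

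**The concern.** None of the protocol's exclusion rules separates dosing lost to an AE from dosing lost for unrelated reasons such as travel or a supply problem. A subject who could not take the drug is informative about tolerability; one who missed doses for an unrelated reason is not. Both are handled alike.

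The subjects at issue have an AE that meets no other DLT criterion, for example a persistent, poorly tolerated Grade 2 event or a Grade 3 cytopenia without fever or bleeding. With cohorts of three, replacement only to two, and explicit permission in Part 1 to choose the next dose on two subjects, the classification of one subject can decide the model's recommendation. Nothing in the protocol or SAP makes the SMC record that classification before the subject disappears from the data.

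**Working it through.** **1. The gap in whole daily doses.** Fraction lost = missed doses / planned doses.

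| Missed | Part 1 (of 21) | Part 2A M8891 (of 22) | Evaluable? | DLT by dose loss? |
|---|---|---|---|---|
| 4 | 19.0% | 18.2% | yes | no |
| 5 | 23.8% | 22.7% | no | no |
| 6 | 28.6% | 27.3% | no | no |
| 7 | 33.3% | 31.8% | (DLT) | yes |

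Cabozantinib in Part 2A (21 doses) follows the Part 1 column. The gap is exactly 5 or 6 missed days.

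**2. Part 2B cabozantinib.** Planned Cycle 1 dose = 60 × 21 = 1260 mg. After d full-dose days and a step to 40 mg with no interruption, the fraction received is (60d + 40(21 − d))/1260.
- d = 2: 880/1260 = 69.8%, so 30.2% is lost
- d = 3: 900/1260 = 71.4%
- d = 8: 1000/1260 = 79.4%
- d = 9: 1020/1260 = 81.0%

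So d = 3 to 8 is below 80% received but not above 30% lost. Section 5.1.3.3 speaks of interruption, so it is unclear whether a reduction counts towards the 30% at all.

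**3. The plan's prior, reproduced.** E(α) = log(0.8/0.2) = 1.386. E(β) = log((log(0.33/0.67) − log 4)/log(210/340)) = log(−2.094/−0.482) = 1.469. Both match Section 8.5.3.1.

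**4. Effect on the model.** I integrated the posterior on a grid with that prior (variances 4, covariance 0.2, reference dose 340 mg), and applied the loss function and the 25% overdose limit of Section 8.5.1. Assumed data: 0/3 DLTs at each of 7, 12, 20 and 35 mg, and one gap subject at 60 mg.

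| Treated at 60 mg | Gap subject | DLTs/n | P(rate > 33%) at 60 mg | Recommended |
|---|---|---|---|---|
| 3, one other DLT | removed | 1/2 | 16.7% | 60 mg |
| | kept, non-DLT | 1/3 | 11.5% | 60 mg |
| | counted as DLT | 2/3 | 38.7% | 35 mg |
| 6, one other DLT | removed | 1/5 | 5.4% | 60 mg |
| | kept, non-DLT | 1/6 | 3.7% | 60 mg |
| | counted as DLT | 2/6 | 16.8% | 60 mg |

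**5. Direction in general.** With true DLT rate p and gap rate g, removal estimates p/(1 − g), keeping as non-DLT estimates p, and counting as DLT estimates p + g. For assumed p = 0.25 and g = 0.10: 0.25/0.90 = 27.8%, 25.0% and 35.0%.

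**6. Wording that does not agree.** Section 5.1.3.2.1 refers to subjects who "do not receive at least 80% of the planned cumulative dose of both treatments", which can mean failing either drug or failing the pair. Table 13 requires the level for each drug. Its label covers Part 2B, but its opening restricts the set to dose escalation cohorts, and Section 8.5.3.3 on Part 2B states no such exclusion. Sections 5.1.3.5.1 and 5.1.3.5.2 bar M8891 modification and cabozantinib interruption for AEs in Cycle 1 of Part 2A, while the interruption DLT presupposes that interruptions happen.

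**The case against.** **Removal biases towards escalation.** A reader might infer this; the documents and the arithmetic do not support it. If the three at 60 mg have no other DLT, P(rate > 33%) at 100 mg is 3.1% with the subject removed (0/2) and 2.4% with the subject kept as a non-DLT (0/3); the model picks 150 mg both times. Removal is the slightly more cautious of the two. Only relabelling the subject as a DLT (1/3) lifts the figure, to about 42%, and holds the model at 60 mg. Removal understates toxicity only if such intolerance ought to count as a DLT, which is a judgement the protocol leaves to the SMC.

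**The SMC can already act.** This largely stands. Section 2 gives the SMC the final decision on DLTs, Section 5.1.3.3 lets it call a clinically significant AE a DLT, and Section 8.5.1 lets it depart from the model when defining the MTD. So the model does not set the dose. But discretion is optional and exclusion is the default. The SMC charter and the separate SMC analysis plan are not among the documents; if they require classification, the point narrows.

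**Part 2B.** A reader might extend step 2 to M8891 reductions. Section 5.1.3.5.1 ties those mainly to events that are themselves of DLT grade, and to recovery after an interruption, so the same arithmetic does not apply. Nor does the high rate of dose reductions that Section 5.2.1.2.1 mentions for the randomised cabozantinib trial say anything about Cycle 1, since no timing is given.

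**The SAP.** It dates from April 2018 and was written for protocol version 2.0, so its difference from the current Table 13 may only reflect age. Its own item 604 still sits badly with its own Table 1. Under SAP Section 8.1 that flag need not mean exclusion, and the final decision is taken at the data review meeting.

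**Conclusion.** The point holds as a gap in the rules. In Parts 1 and 2A, 5 or 6 AE-driven missed doses make a subject non-evaluable without making the subject a DLT, provided that the AE meets no other DLT criterion and the SMC does not intervene. For Part 1, the SAP's analysis set and the protocol's treat the same subject differently. In Part 2B, if the 80% rule does apply to the expansion cohort, a permitted cabozantinib step to 40 mg after 3 to 8 full-dose days is enough to make a subject non-evaluable.

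The documents give no frequency for such subjects. In the assumed cohort of three, the label moves the recommendation between 60 and 35 mg; in the assumed cohort of six it does not move it. The figures rest on the Part 1 prior, cohorts of three and no DLTs below 60 mg. Section 5.1.3.2.1 does report one DLT in the ongoing 60 mg cohort. The Part 2 prior is left to the SMC charter, so no model figure can be given for Part 2A or 2B.

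**What to change.** 1. Reconcile Protocol Sections 5.1.3.1, 5.1.3.2.1, 5.1.3.3, 8.4 (Table 13) and 8.5.3.1 with SAP Section 8.2 and item 604 into one evaluability rule that separates AE-driven from other shortfalls. Settle the both/each wording and the scope of Table 13 in Part 2B.
2. Require the SMC to classify every AE-driven shortfall beyond the evaluability limit as DLT or non-DLT, and to document it, before the model is run, so that none is excluded by default.
3. At each SMC meeting, show the model twice, with these subjects as non-DLTs and as DLTs, as bounds.
4. State whether a toxicity-driven dose reduction in Part 2B affects evaluability.

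Any interruption or dose threshold is for the sponsor to set. The cost is wording and a little more SMC work, with no extra subjects or procedures. The direction of any effect on escalation is not assured: a subject returned as a non-DLT lowers the estimated rate, as 1/2 against 1/3 shows.

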5.1.3.2 Part 2, M8891 combined with Cabozantinib, mRCC

5.1.3.2.1 Part 2A, Dose Escalation

In Part 2A, before Cycle 1 Day 1 of all dose levels, subjects will receive a single dose of M8891 in the morning in fed conditions (Day -1, Cycle 1) and the PK profile of M8891 will be evaluated. Subsequently on Day 1 Cycle 1, subjects will initiate treatment with M8891 combined with cabozantinib QD orally every morning under fasted conditions. Following Cycle 1, all other cycles will start with Day 1 and will include only the 21 days of M8891 combined with cabozantinib.

Subjects will accrue in cohorts of 3 subjects for evaluation of M8891 combined with cabozantinib 60 mg QD (with dosage adjustments to 40 or 20 mg FBE permitted to manage AEs as described in Section 6.5.5). Both drugs will be taken in the morning in fasted conditions. A Bayesian 2-parameter logistic regression model with overdose control will be used to assist the SMC with dose selection for the next cohort and to determine the MTD/RDE of M8891 combined with cabozantinib 60 mg QD for Part 2B.

Three pre-specified dose levels of M8891 are planned (20 mg, 35 mg and 60 mg) combined with 60 mg of cabozantinib. Dose levels may be added or skipped for others that are not part of the pre-specified set but they will never exceed the dose level of M8891 that has already been declared to be safe in Part 1. The dose levels have been chosen based on preliminary data from the ongoing Part 1 of the study. At the time of Amendment 2, M8891 single agent was being investigated at 60 mg QD in subjects with solid tumors. PK^{CC} studies have shown that the 20, 35 and 60 mg QD regimens reached pre-selected exposure (≥ 1500 ng/mL) at steady state while CCI

. Three and 5 Grade ≥ 3 TEAEs have been seen at 20 and 35 mg QD regimen, respectively. One DLT (Grade 4 thrombocytopenia) has been observed in the ongoing 60 mg QD cohort (Refer to the M8891 IB).

Dose escalation of the combination will proceed until the RDE of M8891 is reached in combination with a fixed dose of cabozantinib or dose escalation ends due to occurrence of an MTD, or the SMC decides ending dose escalation following review of safety, tolerability, and PK results, whatever occurs first. The maximum dose of M8891 combined with cabozantinib will not exceed the MTD of M8891 in monotherapy determined in Part 1 of the study.

Subjects will receive M8891 at the assigned dose level and cabozantinib at 60 mg QD until disease progression, unacceptable toxicity, withdrawal of consent, or any criterion for withdrawal from the study (Section 5.5). Unacceptable toxicity in Part 2A is defined as AEs that meet the DLT criteria (Section 5.1.3.3) regardless of when they occur during treatment. An SMC meeting will be held after every cohort to evaluate the safety and tolerability of the combination and to decide on the dose of M8891 for the next cohort.

During Part 2A the selection of the dose will only influence the dose of M8891. Cabozantinib will be given at the approved dose of 60 mg QD. Subjects who develop a DLT during the DLT period, will discontinue treatment with M8891 and will be withdrawn from the study. It will at the Investigator's discretion to continue treatment with cabozantinib or not. The SMC will meet after the completion of each cohort, evaluate the safety of M8891 (combined with cabozantinib), and decide on the recommended dose of M8891. During the treatment phase of the study, guidance for M8891 dose reduction for safety and tolerability is provided in Section 5.1.3.5. Reduction of cabozantinib dose in accordance with the USPI (Refer also to Section 5.1.3.5) will be at the Investigator's discretion based on clinical judgement for safety and tolerability.

At each dose level, the first subject will be observed for DLTs for at least 48 h before commencing dosing of 2 subsequent subjects. The DLT assessment period for Part 2A is the first Cycle (= 22 days, 21 days of M8891 combined with cabozantinib, preceded by 1 day of M8891 alone) of study treatment. Subjects who do not receive at least 80% of the planned cumulative dose of both treatments in Cycle 1 for any reason other than a DLT will not be considered in the DLT evaluation per Bayesian model. Subjects will be replaced to reach a minimum of 2 evaluable subjects per cohort.

In cases where enrollment of the last subject in a dosing cohort is delayed, the SMC may decide (based on available data) upon enrollment and dose for the next dosing cohort before all subjects in a cohort have completed the DLT period. For this subject, the SMC will consider all available data (and any subsequent emerging data) at a subsequent meeting. An ad-hoc meeting will be convened if this subject experiences a DLT.

CCI

